7.1.3 Secondary endpoint analysis

Quantitative secondary endpoints will be analysed on both an intention-to-treat and, separately, a per protocol basis. Results will be presented in terms of between-group differences in either means or medians, with associated 95% confidence intervals.

Categorical data will be analysed using the Chi-squared approach (or Fisher's exact test where appropriate). Ordinal data will be analysed using the Mann Whitney U test or an independent sample t-test. Survival (time-to-event) data will be presented in the form of Kaplan-Meier curves and analysed using the Logrank test (with Cox proportional hazards analysis also performed).

The semi-structured interview component of the study will be analysed using a recognised qualitative approach, such as framework analysis, thematic analysis, or a combination of the two.

Analysis of anonymised radiological images will be performed by two clinicians, who will be blind to treatment allocation. Assessment of pleural effusion size will be performed using a recognised and previously published method. (7)

The comparison of treatment costs between randomisation and being medically fit for discharge will be performed from the perspective of the UK National Health Service, with prices of interventions or treatments being referenced from standard resources.

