4.3.2 Secondary outcomes

- Duration of stay due to pleural infection, as measured by the number of nights in hospital between enrolment and being recorded as medically fit for discharge
- Total inpatient time, as measured by the number of nights in hospital between enrolment and the end of the 90-day post-procedure follow-up period
- Need for step-up therapy, as measured by the difference in proportion of patients requiring intrapleural fibrinolytic therapy or referral for surgical debridement
- All-cause mortality, as measured by the number of patients remaining alive at days 30 and 90 post procedure
- Degree of pleural fluid septation, as measured by the change in bedside thoracic ultrasound septation score from baseline to follow-up days 1, 3, 7, 30 and 90 post procedure
- Pleural effusion size, as measured by the change in radiographic hemithorax opacification from enrolment to discharge, and days 1, 30 and 90 post procedure
- Microbiological yield, as measured by the difference in proportion with positive culture or stain between the control and intervention arms
- Total costs of interventions, as measured by the difference in total cost of treatment for pleural infection (from enrolment to being medically fit for discharge) between two arms
- Quality of life, as measured by the change in EQ-5D subjective health score from baseline to days 30 and 90 post procedure
- Patient experiences, as determined by exploring patients' perceptions and experiences of interventions before and after their procedure through semi-structured interviews

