6.2 RANDOMISATION AND TREATMENT ALLOCATION

6.2.1 Randomisation

Following baseline assessment, randomisation will be performed by a member of the trial team using a web-based system (Sealed Envelope Ltd). Participants will be randomised in a 1:1 ratio to either the control or the intervention arms of the study. The allocation will be determined following minimisation with a random component. The minimisation factors will be:

- Evidence of fluid complexity on thoracic ultrasound – none or mild vs moderate or severe
- Effusion size - $\geq 50\%$ thorax or $< 50\%$ thorax using visual estimation on chest radiograph

Concealed randomisation will reduce selection bias. The sequence of random allocations will be generated by computer and will be concealed from all clinical and research personnel.

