7. STATISTICS AND DATA ANALYSIS

7.1 STATISTICAL ANALYSIS

7.1.1 Sample size

The SPIRIT study is a feasibility study and as such there has been no attempt at formal power or sample size calculation. A recently completed prospective observational study of pleural infection patients requiring drainage (32) would suggest that approximately 150 patients in total would be seen by the selected trial centres over the course of a year. Based on a conservative accrual rate of one of every five patients, a sample size of 30 patients will be used as this is felt to be both sufficient to assess practicability and to suggest the presence of possible between-group differences.

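### Secondary outcomes get unadjusted two-sample tests: the minimisation factors are left out, and change scores are compared without baseline as a covariate

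*Protocol*

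**What the plan says.** Section 6.2.1 of the protocol allocates 1:1 by minimisation: "The allocation will be determined following minimisation with a random component". The two factors are ultrasound fluid complexity (none or mild against moderate or severe) and effusion size (below 50% of the thorax, or 50% and above, judged by eye on the radiograph).

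Section 4.3.2 defines three secondary outcomes as changes from a pre-treatment value: septation score, hemithorax opacification and quality of life. The last is the "change in EQ-5D subjective health score from baseline to days 30 and 90 post procedure". The other quantitative outcomes (length of stay, total inpatient time, step-up therapy, mortality, microbiological yield and cost) have no baseline value of the same measure.

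Section 7.1.3 promises differences in means or medians with 95% confidence intervals. It names chi-squared or Fisher tests for categorical data, the logrank test for time-to-event data with an additional Cox analysis whose covariates are not named, and for the remaining class: "Ordinal data will be analysed using the Mann Whitney U test or an independent sample t-test". The minimisation factors do not appear anywhere in section 7.

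On size, section 7.1.1 says "there has been no attempt at formal power or sample size calculation", but it justifies 30 patients partly as enough "to suggest the presence of possible between-group differences".

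**The concern.** Two separate features of the analysis lose precision.

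- **Minimisation factors left out.** Minimisation makes the arms more alike on the factors than chance would. If the factors predict outcome, the true sampling variance of the difference falls. An unadjusted test still counts the factor variation as noise, so its standard error is too large and its 95% interval covers more than 95% of the time.
- **Baseline subtracted rather than modelled.** A change score fixes the coefficient on baseline at 1. Unless the real slope is close to 1, this adds noise. It also over-corrects any chance baseline difference between the arms. That matters most for EQ-5D, which is not a minimisation factor.

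In addition, two tests are offered for ordinal data with no rule for choosing between them. One is a comparison of means, which treats the steps of an ordinal score as equal.

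At stake is the between-arm information meant to shape a larger trial. With about 15 patients per arm there is little precision to spare.

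**Working it through.** **Stated sample size.** Section 7.1.1 expects "approximately 150 patients in total would be seen by the selected trial centres over the course of a year" and an accrual of one in five: 150 × 1/5 = 30. The figure reproduces. It is accrual arithmetic and implies no precision target. At 1:1 it gives 15 per arm.

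**Unadjusted precision.** For a numeric outcome with standard deviation (SD) s, the 95% half-width is t(0.975; 28 df) × s × √(2/15) = 2.048 × 0.365 × s = 0.748 s.

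**Change score against baseline adjustment.** Let r be the correlation between baseline and follow-up. The protocol does not give it, so every value below is an assumption. With equal SD at the two times:

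- change-score variance per patient = 2(1 − r)s²
- baseline-adjusted variance = (1 − r²)s²
- ratio, adjusted over change = (1 + r)/2
- small-sample penalty for p covariates with N = 30: 27/(27 − p), which is 27/26 for one, 27/25 for two and 27/24 for three

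| r (assumed) | (1+r)/2 | one covariate | two | three |
|---|---|---|---|---|
| 0.3 | 0.65 | 0.675 | 0.70 | 0.73 |
| 0.5 | 0.75 | 0.779 | 0.81 | 0.84 |
| 0.7 | 0.85 | 0.883 | 0.92 | 0.96 |
| 0.8 | 0.90 | 0.935 | 0.97 | 1.01 |

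The two- and three-covariate columns give the factors no credit for explaining variance. Setting the ratio to 1, the gain vanishes at r = 2 × 26/27 − 1 = 0.93 with one covariate and at r = 2 × 24/27 − 1 = 0.78 with three. The penalty also treats the factors as left to chance. Minimisation balances them, so the three-covariate column is somewhat pessimistic.

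As half-widths in SD units with one covariate, change score against adjusted: 0.885 against 0.728 at r = 0.3 (18% narrower), 0.748 against 0.661 at 0.5 (12%), 0.579 against 0.545 at 0.7 (6%) and 0.473 against 0.458 at 0.8 (3%).

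**Minimisation factors alone.** This was simulated: N = 30, two binary factors, 2,500 runs with no treatment effect. The probability of following the minimisation rule is not stated in the protocol; 0.8 is assumed. R² is the assumed share of outcome variance that the factors explain.

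| R² (assumed) | half-width, unadjusted | half-width, adjusted | type I error, unadjusted |
|---|---|---|---|
| 0 | 0.740 | 0.747 (1% wider) | about 0.05 |
| 0.1 | 0.742 | 0.707 (5% narrower) | about 0.04 |
| 0.2 | 0.743 | 0.670 (10% narrower) | about 0.035 |
| 0.4 | 0.748 | 0.580 (22% narrower) | about 0.015 |

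Adjusted type I error stayed near 0.05 throughout (0.042 to 0.059 across settings; the simulation error is about √(0.05 × 0.95/2500) = 0.004).

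**Both together.** At R² = 0.2 and r = 0.5, with a true difference of 0.8 SD (1,500 runs), power was about 0.52 for the change score, 0.56 for the unadjusted follow-up value and 0.76 with factors plus baseline. The simulated baseline was independent of the factors and r applied to the part of the outcome they leave unexplained. The setting is therefore closer to EQ-5D than to septation or opacification, whose baselines overlap with a factor.

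**The case against.** **The analysis plan may settle this.** Covariate lists and rules for choosing a test often sit in the SAP, which is not at hand. Section 7.1.3 never excludes covariates, the Cox model is left open, and an adjusted mean difference would fit the promise of differences with confidence intervals. This stands in part. The protocol does name its tests, however, and apart from the open Cox model they take no covariates and so do not match the allocation method.

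**The quoted sentence is about ordinal data.** Read strictly, no test is named for continuous outcomes such as opacification. The point then rests on the t-test in that sentence being meant for numeric data, which is the natural reading because no other sentence in the section covers such data.

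**Stronger readings that the documents do not support.**

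- A reader might infer that baseline data are ignored. They are not: three outcomes are changes from baseline or enrolment. The fault is subtracting baseline instead of modelling it.
- A reader might take the one-covariate ratios as a gain worth 13% to 48% more patients (1/0.883 and 1/0.675). A model with baseline and both factors gives about 5% to 37% (1/0.956 and 1/0.731) before credit for the factors.
- A reader might treat the factors as categories of the outcome baselines. They are related, but effusion size is graded by eye for allocation, whereas two blinded readers use a published method for the outcome.
- A reader might infer false-positive findings. The error runs the other way.

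**Adjusting everything is not sensible.** Two binary factors make four cells, on average 15/4 = 3.75 patients per arm in each. A stratified risk difference for step-up therapy would often meet empty cells. This stands and limits the fix.

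**Conclusion.** The concern holds in a limited form. The named tests leave out the factors on which allocation is minimised, and three outcomes are compared as change scores without baseline as a covariate. Under assumed r of 0.3 to 0.7 the adjusted variance is 0.68 to 0.88 of the change-score variance with one covariate, or 0.73 to 0.96 with three before any gain from the factors; with three, nothing is gained near r = 0.8 or above. Leaving out the factors costs nothing if they are not prognostic, and about 10% of interval width if they explain a fifth of the variance.

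These sizes rest on assumed correlations, R² values and minimisation probability, and on equal SDs at baseline and follow-up. Baseline adjustment reaches only septation, opacification and EQ-5D, so length of stay can gain from the factors alone. The success criteria in section 7.1.2 are unaffected and no conclusion is made invalid. This is a worthwhile improvement to the secondary analysis.

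**What to change.** Amend section 7.1.3, or state the following in the SAP:

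- **EQ-5D and opacification:** estimate the between-arm difference with 95% CI by linear regression of the follow-up value on arm, baseline value and the minimisation factors. Omit the effusion-size category where continuous baseline opacification is already in the model.
- **Septation score:** name one rank or proportional-odds analysis adjusted for baseline category, with no t-test alternative.
- **Other numeric outcomes without a baseline:** adjust for the two minimisation factors where the data allow.
- **Sparse binary outcomes such as step-up therapy:** report simple unadjusted risk differences with confidence intervals.
- **Sensitivity:** keep the tests now named.

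No new data are needed, because section 6.1.2 collects the baseline measures before randomisation and section 6.2.1 needs both factors to allocate. The cost is wording, one to three degrees of freedom, and intervals about 1% wider if the factors turn out not to be prognostic.

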7.1.4 Interim analysis

No formal interim analysis for feasibility is planned. However, the Data/Safety Monitoring Committee will be asked to review the trial's progress after ten patients have been successfully randomised in order to assess for safety.

8. ADVERSE EVENTS

8.1 DEFINITIONS

8.1.1 Adverse Event (AE)

An untoward medical occurrence in a patient or clinical study subject, which does not have a causal relationship with the trial intervention.

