8.1.2 Adverse Reaction (AR)

An untoward medical occurrence which has a clear causal relationship between the event and the research procedure

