8.1.4 Suspected Unexpected Serious Adverse Reaction (SUSAR)

Any adverse event which is classed as serious and for which there is evidence of a causal relationship with a research procedure, but where that event is unexpected.

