8.2.1 All adverse events/reactions

An AE/AR should be recorded on the dedicated eCRF at the earliest opportunity following the trial team becoming aware of the event. This is most likely to be during the regular follow-up visits.

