8.2.2 Serious adverse events/reactions

Any event which meets the criteria for an SAE should be discussed with the local principal investigator in the first instance. SAEs and SARs should be reported to the Sponsor within 24 hours of the local Principal Investigator (or nominee) becoming aware of the event, using the separate Sponsor-specific SAE form. Events listed in the expected events section below do not need to be reported as SAE/SARs, but will still be recorded as having met the criteria for being serious.

Events which are serious, causally related to a trial procedure (in the opinion of the PI), and which are unexpected (i.e. a SUSAR) should be reported to the Sponsor immediately upon the trial team becoming aware of the event. The Sponsor has a duty to undertake and co-ordinate the expedited reporting required following such events, including to the approving REC.

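### The adverse event and adverse reaction definitions leave possibly related events in neither class, and the SUSAR definition contradicts the adverse event definition

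*Protocol*

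**What the plan says.** Protocol section 8.1 builds its harm classes on causality, but not on one scale.

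- Section 8.1.1 restricts an AE to an occurrence "which does not have a causal relationship with the trial intervention".
- Section 8.1.2 defines an AR as "An untoward medical occurrence which has a clear causal relationship between the event and the research procedure".
- Section 8.1.3 defines SAE and SAR together by seriousness and unexpectedness, without reference to cause.
- Section 8.1.4 defines a SUSAR as "Any adverse event which is classed as serious and for which there is evidence of a causal relationship with a research procedure", adding that the event must be unexpected.

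The operating rules follow in section 8.2. Under 8.2.1, "An AE/AR should be recorded on the dedicated eCRF at the earliest opportunity". Under 8.2.2, "SAEs and SARs should be reported to the Sponsor within 24 hours", apart from events on the expected list in section 8.3. The immediate route to the Sponsor is for serious events that are "causally related to a trial procedure (in the opinion of the PI), and which are unexpected (i.e. a SUSAR").

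**The concern.** An AE is normally the broad class, covering anything untoward that happens to a participant, and ARs are the subset with a suspected link to the procedure. Here the two are written as opposites, one with no link and one with a clear link, and nothing covers the ground between them. In patients who are already unwell with pleural infection, it will often be uncertain whether a deterioration after a procedure was caused by that procedure. Such events may therefore fall in the uncovered ground.

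This bears on the trial's purpose. The lay summary (section 2.3) says that the study asks whether hospitals can offer thoracoscopy safely, and that the procedure carries a slightly higher complication risk than a drain. Section 4.3.2 lists all-cause mortality but no outcome for procedural complications. The section 8 records are thus the main source on procedural harm. If sites class uncertain events differently, any AR figure by arm becomes hard to interpret.

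**Working it through.** No arithmetic underlies the plan here and there is no stated figure to reproduce. The check sets the definitions side by side and asks where an event lands at each degree of relatedness.

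| PI's judgement of relatedness | AE (8.1.1)? | AR (8.1.2)? | SUSAR test on causality (8.1.4), if serious and unexpected |
|---|---|---|---|
| Unrelated | Yes | No | No |
| Possibly related | No: absence of a link not established | No: link not clear | Can be met: some evidence may suffice |
| Probably related | No | No: link not clear | Can be met |
| Clearly related | No | Yes | Met |

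**Step 1: coverage.** AE and AR exclude each other, but together they do not cover all events. The two middle rows belong to neither class. No other text in section 8 says how to class them. A site that must choose can file such an event as an AE, which by definition declares it unrelated, or as an AR, which declares the link clear. Either choice misstates the judgement.

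**Step 2: AE against SUSAR.** Section 8.1.4 starts from "Any adverse event which is classed as serious" and then requires one "for which there is evidence of a causal relationship with a research procedure". Section 8.1.1 has already removed causally related events from the AE class. Read literally, the two conditions cannot sensibly hold together.

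**Step 3: AR against SUSAR.** The AR threshold is a clear link. The SUSAR threshold is evidence of one. The reporting trigger in 8.2.2 is the PI's opinion, with no qualifier. A SUSAR, although named a reaction, therefore need not satisfy the protocol's definition of a reaction.

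**Step 4: what the link is to.** Section 8.1.1 refers to the trial intervention, 8.1.2 and 8.1.4 to the research procedure, and 8.2.2 and 8.3 to a trial procedure. None is defined in section 8. Sections 4.1, 6.4.3 and 9.3 describe the allocated procedures and the biopsies as routine or standard, and section 6.4.4 has a separate heading for research samples, so the choice of term is not neutral.

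**Step 5: recording and reporting.** AEs and ARs go on the same eCRF. SAEs and SARs go to the Sponsor within the same 24 hours, and 8.1.3 does not ask about cause. An event with the wrong label is therefore still likely to be recorded and, if serious and not on the expected list, reported. What suffers is the label.

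**Sensitivity to one event.** With 30 patients randomised 1:1 (section 4.2), each arm has about 30 / 2 = 15. Moving one patient's event between AE and AR changes that arm's proportion with a reaction by 1/15 = 6.7 percentage points. This is only the step size in a small trial. It does not estimate how many events would be misclassified.

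**The case against.** The strongest reply is that the labels do little work: recording and urgent reporting largely do not depend on whether an event is called an AE or an AR. That stands, and it limits the point to classification. Four stronger readings are tempting, and the protocol does not support them.

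- *A reader might infer that SUSARs will be under-counted.* They need not be. Sections 8.1.4 and 8.2.2 set their own causality test, which is lower than the clear link required of an AR. The supported statement is that 8.1.4 conflicts with 8.1.1.
- *A reader might infer that possibly related events will go unrecorded.* The shared eCRF and the shared serious-event route make that unlikely. One item in section 8.3 does turn on cause: a delayed discharge counts as expected unless a complication directly related to a trial procedure explains it. That is separate wording. It adds another causality phrase to align but does not turn the definitional gap into a general loss of events.
- *A reader might infer that thoracoscopy complications fall outside section 8 because thoracoscopy is called routine care.* Section 8.3 lists infection related to thoracoscopy or drain insertion, so these procedures are plainly in scope. The mixed terms are untidy and do not create an exemption.
- *A reader might infer that the DMC will see a reaction count that is too low.* Sections 7.1.4 and 11.3 ask the DMC to assess safety but do not say that it receives AR tallies rather than all events. An AR rate is also not a listed outcome.

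In addition, the Appendix 3 flow chart is not reproduced in the text available and the eCRF is not shown. Either may contain a causality step that helps sites. Neither would remove the conflict between 8.1.1 and 8.1.4.

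**Conclusion.** The point holds as an internal inconsistency in the safety definitions. The AE and AR classes are not exhaustive, 8.1.4 contradicts 8.1.1, three causality thresholds are in use across 8.1.1, 8.1.2 and 8.1.4, and the causal reference changes between sections. The likely consequence is that procedure-related harms are classed wrongly or inconsistently, so that a tally of reactions could be too low or could differ between sites. The size cannot be derived from the protocol, since it depends on how many events are of uncertain cause and how each site resolves them. The conclusion rests on the wording of section 8 alone and assumes that Appendix 3 and the eCRF do not override that wording. It is worth correcting because the remedy is cheap and the trial is meant to inform whether thoracoscopy can be offered safely.

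**What to change.** Amend section 8.1 so that the classes nest:

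- **AE:** any untoward medical occurrence in a participant, whether or not related to a trial procedure.
- **AR:** an AE with at least a reasonable possibility of being related to a trial procedure.
- **SUSAR:** a serious AR that is unexpected.

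Use the single term *trial procedure* throughout section 8, and state that it includes the allocated thoracoscopy or drain insertion and any research sampling. Bring the causality wording in 8.2.2 and 8.3 into line. Check that the Appendix 3 flow chart and the eCRF relatedness field follow the same threshold, and change them only if they do not already match.

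The cost is a short wording amendment and, at most, one revised eCRF field. The reported reaction rate may be somewhat higher, because events of uncertain cause would now count as reactions.
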